# 3.1.2.1 Analysis Visit Windows for Efficacy Endpoints

Table 1a. Visit Windows for SNOT-22

Analysis Visit	Target Analysis Day	Low Analysis Day	High Analysis Day
Week 2	Aday 15	Aday 2	Aday 21
Week 4	Aday 29	Aday 22	Aday 35
Week 6	Aday 43	Aday 36	Aday 49
Week 8	Aday 57	Aday 50	Aday 70
Week 12	Aday 85	Aday 71	Aday 98
Week 16	Aday 113	Aday 99	Aday 126
Week 20	Aday 141	Aday 127	Aday 154
Week 24	Aday 169	Aday 155	Aday 182
Week 28/follow-up*	Aenday 28	Aenday 1	Aenday 31

\* post-treatment follow-up.

Table 1b. Visits for Weekly 3CS and 4 Individual Cardinal Symptom Scores

Analysis Visit	Analysis Week (Days)
Week 1	Aday 2 - Aday 8
Week 2	Aday 9 - Aday 15
Week 3	Aday 16 - Aday 22
Week 4	Aday 23 - Aday 29
Week 5	Aday 30 - Aday 36
Week 6	Aday 37 - Aday 43
Week 7	Aday 44 - Aday 50
Week 8	Aday 51 - Aday 57
Week 9	Aday 58 - Aday 64
Week 10	Aday 65 - Aday 71
Week 11	Aday 72 - Aday 78
Week 12	Aday 79 - Aday 85
Week 13	Aday 86 - Aday 92
Week 14	Aday 93 - Aday 99
Week 15	Aday 100 - Aday 106
Week 16	Aday 107 - Aday 113
Week 17	Aday 114 - Aday 120
Week 18	Aday 121 - Aday 127
Week 19	Aday 128 - Aday 134
Week 20	Aday 135 - Aday 141
Week 21	Aday 142 - Aday 148
Week 22	Aday 149 - Aday 155

Week 23	Aday 156 - Aday 162	
Week 24	Aday 163 - Aday 169	
Week 25/follow-up*	Aenday 1 - Aenday 7	
Week 26/follow-up*	Aenday 8 - Aenday 14	
Week 27/follow-up*	Aenday 15 - Aenday 21	
Week 28/follow-up*	Aenday 22 - Aenday 28	

Note: score for a week is the average of the non-missing daily scores over the 7-day period of the week. If less than 4 daily scores are available for a week, the individual CS score will be considered missing for that week.

Table 1c. Visit Windows for CRS-PRO

Analysis Visit	Target Analysis Day	Low Analysis Day	High Analysis Day
Week 2	Aday 15	Aday 12	Aday 18
Week 3	Aday 22	Aday 19	Aday 25
Week 4	Aday 29	Aday 26	Aday 35
Week 6	Aday 43	Aday 36	Aday 49
Week 8	Aday 57	Aday 50	Aday 70
Week 12	Aday 85	Aday 71	Aday 98
Week 16	Aday 113	Aday 99	Aday 126
Week 20	Aday 141	Aday 127	Aday 154
Week 24	Aday 169	Aday 155	Aday 182
Week 28/follow-up*	Aenday 28	Aenday 1	Aenday 31

\* post-treatment follow-up.

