3. STUDY OBJECTIVES AND ENDPOINTS

The study objectives and endpoints are:

Study Objectives	Study Endpoints
Primary	
To evaluate unexpected serious adverse events related to LYR-220	- Product-related unexpected serious adverse events
Pharmacokinetics	
To evaluate the pharmacokinetics of LYR-220	 Plasma MF concentrations at 1 hour (±10 minutes) post study treatment administration and at Days 2 or 3, and Days 5 or 8, and Weeks 4, 12, 16 or 20, 24, and 25
Secondary - Safety	
To evaluate the safety and tolerability of LYR-220	- Treatment-emergent adverse events (TEAEs) and serious adverse events (TESAEs) through Week 28
	- Clinically significant abnormal laboratory values (hematology and chemistry) through Week 25
	- Newly identified or worsened endoscopic findings (epistaxis and mucosal injury) in ethmoid cavity through Week 25
	- Clinically significant increase of IOP through Week 25
	A clinically significant increase of IOP is defined as IOP in 1 or both eyes >23 mm Hg or an increase of IOP from Baseline in one or both eyes \geq 10 mm Hg.
	- Newly identified or worsened cataract in 1 or both eyes by slit-lamp examination through Week 25
Secondary - Efficacy	
To evaluate the efficacy of LYR- 220 in improving total SNOT-22 and subdomain scores through	- Change from baseline (CFBL) in SNOT-22 total and subdomain scores at Weeks 2, 4, 6, 8, 12, 16, 20, 24, and 28
Week 28	The SNOT-22 questionnaire is a 22-item disease- specific quality of life instrument validated for use in CRS. Each symptom is scored as it has been over the past 2 weeks on a 6-point scale as follows: $0 = no$ problem, $1 = very$ mild problem, $2 = mild$ or slight

	problem, 3 = moderate problem, 4 = severe problem, 5 = problem as bad as it can be.
To evaluate the efficacy of LYR- 220 in improving 3CS and individual cardinal symptom score through Week 28	 CFBL in the average composite score over the preceding 7 days of 3 cardinal symptoms (3CS) and individual cardinal symptom scores at Weeks 2, 4, 6, 8, 12, 16, 20, 24, and 28
	The 3 cardinal symptoms include nasal blockage/obstruction/congestion, facial pain/ pressure, and anterior/posterior nasal discharge. Each symptom is scored on a 0-3 scale as follows: $0 = none$, $1 = mild$, $2 = moderate$, and $3 = severe$.

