6.5 Removal Procedure

Subjects will have the LYR-220 drug matrices removed bilaterally at the Week 24/EOT visit or earlier in an unscheduled early termination (ET) visit, if medically warranted according to the treating physician's discretion (eg, require sinonasal surgery as rescue treatment or use of any other MF medications). The removal procedure will be performed under endoscopic visualization after local anesthetic and decongestants applied to each nostril. Standard surgical tools are used to remove LYR-220. LYR-220 is made of polymers designed to gradually soften over time. Care should be taken to remove LYR-220 in 1 piece or in sections should any disintegration of LYR-220 occur.

To maintain blinding through the end of the study, subjects enrolled in the sham procedure group will undergo a sham removal procedure either at the scheduled Week 24 visit or earlier in an unscheduled early termination (ET) visit if the subject requests early study product removal.

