Enrolled subjects will be asked to complete a daily ePRO questionnaire to assess the severity of the 4 CS of CRS (nasal blockage/obstruction/congestion, facial pain/pressure, anterior/posterior nasal discharge, and loss of smell). In addition, the ePRO will capture use of daily saline irrigation by the subjects. Subjects will also complete 2 validated CRS-specific quality of life questionnaires, the SNOT-22 and CRS-PRO, at Screening, on Day 1 before treatment, and at Weeks 2, 4, 6, 8, 12, 16, and 20, at Week 24 before matrix removal, and at Week 28/EOS. CRS-PRO will also be assessed at Day 8 and Week 3. The PGIS will be administered on Day 1

(pretreatment) and at Weeks 8, 16, and 24/EOT. The PGIC will be assessed at Week 24/EOT. At Week 28/EOS visit, an end-of-study questionnaire will be administered.

Ethmoid cavity opacification will be assessed by CT scans obtained during Screening (or using a historical scan taken within 3 months of Screening) and at Week 25 visit, unless medically contraindicated. Subjects will be instructed to stop use of saline rinse approximately 24 hours prior to the scheduled sinus CT. Daily saline irrigation should then continue following the sinus CT. If a subject is experiencing or recovering from a cold, acute exacerbation of nasal allergy, or upper respiratory tract infection at Week 25 visit, the CT assessment should be performed 4 weeks after resolution of the adverse event. If a subject early terminates from the study or requires SCS or sinonasal surgery as rescue treatment during the study, every attempt should be made to perform the follow-up CT before subject receives the rescue treatment.

LYRA THERAPEUTICS, INC. STUDY LYR-220-2021-001

VERSION 4.0 (30 AUG2022)

Enrolled
jects
Sub
s for
Assessment
$\mathbf{0f}$
hedule
Sc
Ξ
Table

		2															
		_						Treat	Treatment Stage	age						Post-	4
Evaluation	ing & Run-In	dure Day														Treatment Stage	ient je
Visits #	1	2	3	~	4		⊢	⊢	5	⊢	F	9	7/7	F	œ	6	10/T p
Study Day/Week	DAY - DAY - 28 (Day - 28 to Day 0)	DAY 1 (Day 1)	DAY 2 (Day 2)	DAY 3 (Day 3)	DAY 5 (Day 5)	DAY 8 (Day 8)	WK 2 (Day 15±1)	WK 3 (Day 22±2)	WK 4 (Day 29±3)	WK 6 (Day 43±3)	WK 8 (Day 57±3) ª	WK 12 (Day 85±3)	WK 16 (Day 113±3) ª	WK 20 (Day 141±3) ª	WK 24/EO T/ET (Day 169±7)	WK 25 (5-9 days after T)	WK 28 (EOS) (25-31 days after EOT)
Informed Consent	×c																
Demographics	×																
Medical History	Х																
Vital Signs	Х																

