## 2.3.3 Secondary Efficacy Endpoints

The secondary efficacy endpoints are:

- 1. Change from baseline (CFBL) in SNOT-22 total and subdomain scores at Weeks 2, 4, 6, 8, 12, 16, 20, 24, and 28/Follow Up.
- 2. CFBL in the 7-day average composite score of 3CS and individual cardinal symptom scores at Weeks 2, 4, 6, 8, 12, 16, 20, 24, and 28/Follow Up.
- 3. CFBL in the 7-day average score of loss of smell for subjects with baseline score ≥2 at Weeks 2, 4, 6, 8, 12, 16, 20, 24, and 28/Follow Up.
- 4. CFBL in CRS-PRO total and subdomain scores at Weeks 2, 3, 4, 6, 8, 12, 16, 20, 24, and 28/Follow Up.
- 5. Time to first rescue treatment recommendation through Week 28/Follow Up.
- 6. Systemic/oral corticosteroid use or sinonasal surgery recommendation through Week 28/Follow Up.
- CFBL in bilateral percent ethmoid cavity opacification by CT at Week 25/Follow Up.
- 8. CFBL in PGIS score at Weeks 8, 16, and 24.
- 9. PGIC score at Week 24.
- 10. No longer a candidate for revision surgery.
- 11. CFBL in nasal inflammatory marker levels at Week 25/Follow Up.

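### SAP Table 1b fixes the Week 24 diary week at Days 163–169 while removal is allowed from Day 162, so an early but compliant removal leaves the Week 24 3CS either missing or partly to wholly post-removal

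*SAP*

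**What the plan says.** The protocol (Section 3) defines the diary endpoint as "CFBL in the average composite score over the preceding 7 days of 3 cardinal symptoms (3CS") at Weeks 2 to 28. SAP 2.3.3 restates it as "CFBL in the 7-day average composite score of 3CS and individual cardinal symptom scores". SAP Table 1b (Section 3.1.2.1) assigns Week 24 to "Aday 163 - Aday 169", where Aday 1 is the insertion day. It counts the follow-up weeks from end of treatment instead: Week 25 is "Aenday 1 - Aenday 7" and Week 28 is "Aenday 22 - Aenday 28".

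Removal takes place at the Week 24/EOT visit, or earlier at an ET visit. Protocol Table 1 heads that visit "WK 24/EO T/ET (Day 169±7"). Control subjects have a "sham removal procedure either at the scheduled Week 24 visit" or at an earlier ET visit (Protocol 6.5). SNOT-22 and CRS-PRO are collected "at Week 24 before matrix removal, and at Week 28/EOS" (Protocol 8.1).

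Three further provisions bear on the point:
- A weekly score based on fewer than four daily scores is missing (SAP 3.1.4.8 and 3.1.4.9).
- SAP 3.1.2 treats visits from 1 to 31 days after end of treatment as follow-up, and the Table 1b footnote labels Weeks 25–28 as post-treatment.
- SAP 3.1.1 sets Aenday 0 at the last dose day. It does not say what that means for a single implanted matrix.

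**The concern.** One window is anchored to insertion and the next to end of treatment, while the event that separates them may fall anywhere in a 15-day range. When removal comes before Day 169, the two windows overlap, and nothing in the SAP says which one takes a diary entry that meets both.

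The results exposed are the Week 24 change from baseline in 3CS and individual symptoms, the conversion endpoint where it relies on a Week 24 3CS of 4 or lower (SAP 3.1.4.16), and the 3CS output of the primary lock (SAP 4.2). That lock is triggered by completion of the Week 24 visit, which can come up to 7 days before the last diary day of the Table 1b week.

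The other Week 24 windows do not have this problem. Those for SNOT-22 and CRS-PRO (Aday 155–182) and for PGIS and PGIC (Aday 141–196) contain the whole visit window, and SNOT-22 and CRS-PRO are completed before removal. Under the literal table, one subject could have an on-treatment Week 24 SNOT-22 and an off-treatment Week 24 3CS. Only the LYR-220 arm loses a matrix and drug at removal.

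**Working it through.** **Inputs.** Week 24 diary week, Aday 163–169 (SAP Table 1b). Removal day R = 169±7, so 162–176, which is 15 permitted days (Protocol Table 1). Minimum of four entries (SAP 3.1.4.9). Aenday 0 is taken as R. The entry on day R is taken as pre-removal, because the diary is completed in the morning and questionnaires at clinic visits come before any intranasal procedure (Protocol 8.4.1 and 8.4.1.1). The diary is taken as complete.

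**The plan's own figure.** Table 1b follows week k = Day 7(k−1)+2 to Day 7k+1. For k = 24: 7×23+2 = 163 and 7×24+1 = 169. The stated window is reproduced.

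**Overlap for scheduled removal, R = 162 to 168.** Entries up to and including R number R−162. Entries after R number 169−R.

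| R | Entries to R | Entries after R | Week 24 if entries after R go to follow-up |
|---|---|---|---|
| 162 | 0 | 7 | missing |
| 163 | 1 | 6 | missing |
| 164 | 2 | 5 | missing |
| 165 | 3 | 4 | missing |
| 166 | 4 | 3 | scored on 4 |
| 167 | 5 | 2 | scored on 5 |
| 168 | 6 | 1 | scored on 6 |
| 169–176 | 7 | 0 | scored on 7 |

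For R = 162–168, every entry after R lies within R+1 to R+7, so it also meets the Week 25 window. Week 28 starts at R+22, which is Day 184 or later, so scheduled removals do not affect it.

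- *Follow-up takes the shared entries:* 4 of the 15 permitted days (162–165) make Week 24 missing. On Day 166 a single skipped entry does the same. If the removal-day entry were not counted, Day 166 would have three entries and be missing too.
- *Literal table:* 7 of the 15 permitted days (162–168) put post-removal entries into Week 24. If post-removal daily scores differ by d points, the subject's Week 24 score shifts by d(169−R)/7, for example 4d/7 = 0.57d at R = 165. The arm mean shifts by between 0 (all removals on Day 169 or later) and 1.0d (all on Day 162).

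These are counts of permitted days, not proportions of subjects. The documents give neither the distribution of R nor d.

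**Treatment ending early, on day E.** Week 28 covers E+22 to E+28. It overlaps Week 24 (163–169) by 7−|E−141| entries for E = 135–147, and Week 20 (135–141) by 7−|E−113| entries for E = 107–119. At E = 141 and E = 113 respectively, all seven entries coincide.

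**The case against.** The strongest reply is that the SAP already leans towards an answer. SAP 3.1.2 and the Table 1b footnote point shared entries to follow-up. A missing Week 24 is then covered three times for change from baseline, because SAP 3.4.2.2 applies the SNOT-22 methods to the 3CS: the MMRM under MAR, and the ANCOVAs with multiple imputation and with LOCF. This largely stands. It reduces the cost for those endpoints to lost precision and reliance on those missing-data methods. It does not remove the defect: SAP 3.1.2 speaks of visits rather than diary days, and a compliant subject with a full diary still loses a named endpoint value. SAP 3.4.2.10 states no handling of a missing 3CS for the conversion endpoint. That gap is general, but Table 1b feeds it.

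It can also be said that Days 163–169 are simply the nominal week, that the protocol does not say the seven days must precede the visit, and that CT and marker efficacy are measured 5–9 days after removal anyway. These points are fair. However, CT and markers are planned as post-removal measures, whereas the Week 24 3CS is labelled a treatment-period score. The first entry after removal recalls 24 hours that partly precede removal, so a constant d is only an approximation.

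A reader might infer that the Week 24 3CS comparison is contaminated and biased. The documents do not support that: it requires the less-supported reading, removals before Day 169 and a non-zero d, none of which they establish. A reader might also infer that the treatment-policy strategy (ICE2, SAP 3.4.2.1.1) settles the matter. It covers premature discontinuation, not removal within the visit window, and does not assign data to a visit. The separate programming specifications (SAP 6), which are not among the documents, may contain a rule.

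**Conclusion.** The overlap is real and follows from the stated windows alone. Under the better-supported reading, removal on Days 162–165 makes the Week 24 3CS and symptom scores missing despite a complete diary. Under the literal table, removal on Days 162–168 puts 7 to 1 post-removal entries into them. The day counts are certain given a complete diary, Aenday 0 on the removal day and a pre-removal entry that day.

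The consequence is uncertain. The number of subjects affected, and the size and direction of any shift, cannot be computed. If nobody was removed before Day 169, the scheduled-removal problem disappears. With about 20 subjects per arm, one subject reclassified on the conversion endpoint moves that arm's rate by 1/20 = 5 percentage points, unless the subject qualifies by CT. Removals on Days 169–176, Week 24 SNOT-22, CRS-PRO and PGIS at scheduled removal, and the primary safety endpoint are not affected. In an unpowered Phase II study with a safety primary endpoint this is a limited defect, but it is cheap to correct and worth correcting.

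**What to change.** 1. For subjects removed or sham-removed at the scheduled Week 24 visit (Days 162–176), define the Week 24 diary week as the seven days ending on the earlier of R and Aday 169, using the pre-removal entry on day R. Keep the four-entry rule. Removals on Days 169–176 keep Aday 163–169.
2. Start the follow-up weeks at R+1. In SAP 3.1.1, define Aenday 0 as the day of removal, sham removal or dislodgement of the second matrix, in line with the heading of SAP 3.3.9.
3. For treatment ending before Day 162, note that the end-of-treatment-anchored Week 28 can coincide with insertion-anchored endpoint weeks, and state which visit such entries feed.

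The cost is a few SAP sentences and reprogramming of data already collected, with no protocol change. The downside is that, for early removals, Week 24 shares 169−R entries with Week 23 (all seven at R = 162). Week 23 appears in Table 1b but is not a listed endpoint week. For removals after Day 169, the R−169 diary days from Day 170 to R stay in no window, as they do now. If the change is made after the primary lock, label it post hoc, as SAP 4.2 requires.

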1. SYNOPSIS

Sponsor	Lyra Therapeutics, Inc.	
	[name]	
	[name]	
Protocol Title	BEACON: A Phase II, Patient-blinded, Two-part,	
	Randomized, Parallel-group Trial to Evaluate the Safety,	
	Tolerability, Pharmacokinetics, and Efficacy of LYR-220 in	
	Chronic Rhinosinusitis (CRS) Patients Who Have Had a	
	Prior Ethmoidectomy	
Protocol Number	LYR-220-2021-001	
Phase of Development	Phase II	
Investigational Product	LYR-220-32 System (7500 µg) and LYR-220-16 System	
	(7500 µg)	
Active Ingredient	Mometasone furoate (MF)	
Trial Location	Worldwide	
Number of Sites	Up to 25 sites	
Study Population	Adult CRS patients who have had a prior bilateral total	
	ethmoidectomy	
Estimated Number of Subjects	Approximately 50 subjects	
Study Endpoints	Study Endpoints	
Primary		
- Product-related unexpected serious adverse events		
Pharmacokinetics		
- Plasma MF concentrations at 1	hour post study treatment administration and at Days 2 or 3,	
Days 5 or 8, and Weeks 4, 12, 16 or 20, 24, and 25		
Secondary – Safety		
- Treatment-emergent adverse events (TEAEs) and serious adverse events (TESAEs) through		
Week 28		
- Clinically significant abnormal laboratory values (hematology and chemistry) through Week 25		
- Newly identified or worsened endoscopic findings (epistaxis and mucosal injury) in ethmoid		
cavity through Week 25		

- Clinically significant increase of IOP through Week 25

A clinically significant increase of IOP is defined as IOP in 1 or both eyes >23 mm Hg or an increase of IOP from Baseline in 1 or both eyes ≥ 10 mm Hg.

- Newly identified or worsened cataract in 1 or both eyes by slit-lamp examination through Week 25

Secondary – Efficacy

- Change from baseline (CFBL) in SNOT-22 total and subdomain scores at Weeks 2, 4, 6, 8, 12, 16, 20, 24, and 28

The SNOT-22 questionnaire is a 22-item disease-specific quality of life instrument validated for use in CRS. Each symptom is scored as it has been over the past 2 weeks on a 6-point scale as follows: 0 = no problem, 1 = very mild problem, 2 = mild or slight problem, 3 = moderate problem, 4 = severe problem, 5 = problem as bad as it can be.

- CFBL in the average composite score over the preceding 7 days of 3 cardinal symptoms (3CS) and individual cardinal symptom scores at Weeks 2, 4, 6, 8, 12, 16, 20, 24, and 28

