4.1.3 Post-treatment Follow-Up Stage

All subjects will undergo a 1-week post-treatment follow-up visit (Week 25 visit). AEs, concomitant medications/procedures, endoscopy, nasal swabs, ophthalmologic assessments, CT, and other scheduled assessments will be performed at Week 25 visit. In addition, subjects will complete a 4-week post-treatment follow-up by telephone or in-clinic visit [Week 28/end-of-study (EOS)]. End of study assessments include AEs, concomitant medications/procedures, and final ePROs (4CS, SNOT-22, CRS-PRO, and End-of-Study Questionnaire).

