### 3.1.1 Analysis Day

Analysis day for analysis visit windows (i.e., "Aday") will be calculated from the date of study treatment (LYR-220 or sham) administration. The day of study treatment administration will be Aday 1, and the day immediately before Aday 1 will be Aday -1.

Additionally, analysis day relative to the last dose day (i.e., "Aenday") will be calculated from the date of last dose of study treatment. The day of last dose of study treatment will be Aenday 0, and the day immediately after Aenday 0 will be Aenday 1. Data collected up to 31 days after end of treatment will be included in the analysis.

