# 3.1.4.9 Weekly 3CS Score through Week 28/Follow Up

The 3CS score for a week is the average of the non-missing daily 3CS scores over the 7-day period of the week. If less than 4 daily 3CS scores are available for a week, the 3CS score will be considered missing for that week.

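### The SAP's fixed Week 28 diary week (Aenday 22-28) can cost subjects with an on-time but early end-of-study visit their Week 28 cardinal-symptom scores; a fallback for EOS on days 25-27 would prevent this

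*SAP*

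**What the plan says.** **Diary week.** SAP 3.1.2.1, Table 1b, assigns daily cardinal-symptom entries to fixed calendar weeks. Week 28/follow-up is "Aenday 22 - Aenday 28", and Week 27/follow-up is the 7 days before it (Aenday 15-21). SAP 3.1.1 sets the count: "The day of last dose of study treatment will be Aenday 0, and the day immediately after Aenday 0 will be Aenday 1".

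**Minimum entries.** For the composite, SAP 3.1.4.9 states: "If less than 4 daily 3CS scores are available for a week, the 3CS score will be considered missing for that week". The note to Table 1b sets the same minimum for individual symptoms: "If less than 4 daily scores are available for a week, the individual CS score will be considered missing for that week". Loss of smell is one of these.

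**Visit window.** Protocol 8.1, Table 1, places the Week 28/EOS contact "25-31 days after EOT". Protocol 4.1.3 lists among the EOS assessments the "final ePROs (4CS, SNOT-22, CRS-PRO, and End-of-Study Questionnaire".

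**Endpoint.** The protocol synopsis defines the endpoint at each named week, including Week 28, as change in the "average composite score over the preceding 7 days of 3 cardinal symptoms (3CS" and in the individual symptom scores.

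**Other questionnaires.** The Week 28 windows for SNOT-22 and CRS-PRO (SAP Tables 1a and 1c) run from Aenday 1 to 31 and so cover any permitted EOS day.

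**The concern.** The diary week is fixed, but the visit that appears to close the diary can move by 3 days either way. When EOS falls before day 28, part of the fixed week lies after the last diary entry. Nothing in the SAP then brings in the diary days just before day 22, which are filed under Week 27/follow-up. A subject seen inside the protocol window can therefore lose the Week 28 score because of the visit date together with one to three missed entries.

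Week 28 is a named time point for 3CS, the individual symptoms and loss of smell, and one of the two time points in the ANCOVA analyses that SAP 3.4.2.2 carries over from SNOT-22. A lost score is treated as missing at random in the MMRM, multiply imputed in one ANCOVA, or replaced by an earlier value in the LOCF analysis, although adjacent diary days are on file.

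**Working it through.** **Inputs from the documents.** Week 28 diary days 22-28 (SAP Table 1b); minimum of 4 entries (SAP Table 1b note and 3.1.4.9); EOS on days 25-31 (Protocol 8.1, Table 1); one diary entry each morning (Protocol 8.4.1.1). About 40 subjects in Part 2.

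**Assumptions.** Aenday 0 is the removal day. The SAP refers to the last dose of a single-administration product, so this is a reading, though it fits the SAP's use of end of treatment for follow-up visits. The last entry is made on the EOS morning. Daily completion is independent with probability p; the documents give no rate, so p = 0.80, 0.85 and 0.90 are shown. They give no distribution of EOS days either.

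**Step 1: the plan's own figure.** 28 - 22 + 1 = 7 days, which matches the stated 7-day week.

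**Step 2: entries possible.** For EOS on day d, n = min(d, 28) - 22 + 1. The score is lost once n - 3 entries are missed.

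**Step 3: chance of loss.** P(loss) = P(Binomial(n, p) < 4). For n = 4 this is 1 - p^4; at p = 0.85, 1 - 0.522 = 0.478.

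| EOS day | n | Missed entries that lose the score | p = 0.80 | p = 0.85 | p = 0.90 |
|---|---|---|---|---|---|
| 25 | 4 | 1 | 59.0% | 47.8% | 34.4% |
| 26 | 5 | 2 | 26.3% | 16.5% | 8.1% |
| 27 | 6 | 3 | 9.9% | 4.7% | 1.6% |
| 28-31 | 7 | 4 | 3.3% | 1.2% | 0.3% |

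If the EOS-morning entry is not made, EOS on day 25 leaves 3 possible entries and the score cannot be computed at all.

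**Step 4: overall missingness, two assumed spreads of EOS days.**

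- Even over days 25-31, p = 0.85: (47.8 + 16.5 + 4.7 + 4 × 1.2)/7 ≈ 10.6% (unrounded inputs), against 1.2% with 7 days for everyone. For 40 subjects: 40 × (0.106 - 0.012) ≈ 4 more missing scores. The same spread gives 15.5% against 3.3% at p = 0.80, and 6.5% against 0.3% at p = 0.90.
- Clustered at day 28 (weights 1, 2, 3, 4, 3, 2, 1 for days 25 to 31), p = 0.85: (47.8 + 2 × 16.5 + 3 × 4.7 + 10 × 1.2)/16 ≈ 6.7%. For 40 subjects: 40 × (0.067 - 0.012) ≈ 2 more.
- Every EOS on day 28 or later: no added loss.

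The 40-subject counts also assume that all Part 2 subjects reach EOS.

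**The case against.** A reader might infer that the SAP contradicts the protocol's endpoint. The documents do not support that. The protocol speaks of the preceding 7 days at Week 28 but does not tie them to the actual visit date. With removal as day 0, days 22-28 are exactly the 7 days ending at nominal Week 28, and Table 1b treats every week in the same way. A fixed week is a fair reading of the protocol, and so is a week anchored to the visit.

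A reader might also count it as a fault that entries on days 29-31 go unused. Subjects with EOS on those days have the whole of days 22-28 available, so leaving out the later entries costs no score.

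Two further objections have weight. First, the diary ending at EOS is an inference from the list of final questionnaires. No stop rule is stated, and EOS may be a telephone contact, so device return need not end the diary. If entries continued to day 28, the loss would not arise. Second, the consequence is limited: the affected subject stays in the MMRM through earlier visits, one rule applies to both arms, and a score lost because of a visit date has no evident link to symptoms, so missing at random is plausible. Scores based on 4-6 entries also meet the SAP's own minimum.

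What remains is the day count. Within the permitted visit window, the number of possible entries can fall to the bare minimum, and the SAP has no rule for that case.

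**Conclusion.** The gap is real and small. The counts of 4, 5 and 6 possible entries for EOS on days 25, 26 and 27 follow from the documents once Aenday 0 is removal and the diary ends with the EOS-morning entry. The percentages rest on assumed completion rates, and the overall figure (about 7-11% missing instead of 1% at 85% completion, or roughly 2-4 more of 40 subjects) also rests on an assumed spread of EOS days.

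The cost is some precision in the Week 28 3CS, individual-symptom and loss-of-smell comparisons, which are secondary and taken four weeks after matrix removal. It would be going too far to infer bias between arms, because nothing in the plan shows it. The Week 24 scores, the Week 24 3CS criterion in the revision-surgery endpoint, and the safety analyses are not affected. The change is worth making because it recovers collected data at almost no cost, not because the study's conclusions depend on it.

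**What to change.** Keep Aenday 22-28 as the default Week 28/follow-up row in Table 1b and add a footnote: when EOS occurs on Aenday 25-27, the Week 28/follow-up score uses the 7 diary days ending on the EOS day (19-25, 20-26 or 21-27), still with at least 4 entries, and these days count for Week 28 rather than Week 27/follow-up. Subjects with EOS on day 28 or later, or with no EOS contact, stay on Aenday 22-28. Limiting the rule to early EOS leaves subjects who already have 7 days unchanged and still gives a window to anyone who misses the EOS contact. State also whether the diary ends on the EOS day.

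**Effect.** With EOS on day 25, the possible entries rise from 4 to 7, and at 85% completion the chance of loss falls from 47.8% to 1.2%.

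**Cost.** One footnote and the matching program change. The Week 28 diary week moves up to 3 days earlier for early-EOS subjects, and their Week 27 keeps 4, 5 or 6 days (15-18, 15-19 or 15-20). Week 27 is not a named endpoint time point. Under SAP 4.2, the change would have to precede the primary lock analysis or be labelled post hoc.
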